Since the standard of care is narcotic usage to manage the significant pain that complex spinal surgery causes, it is understandable that methadone could be a desirable therapy to promote sustained pain control and early ambulation in these patients. It is our hypothesis that methadone use intraoperatively will result in earlier time to ambulate post op and better ability to participate with post-operative PT evaluation, lower narcotic usage, earlier discharge, and improved scores on clinical outcome scales including the Oswestry Low Back Pain Disability Questionnaire and the Short Form 36 Health Survery. It is also foreseeable that since methadone would be administered while the patient was sedated intraoperatively, it could prevent the association between the analgesia and euphoria that may result from self- or nurse-administered narcotics, such as with a PCA, which could promote early tolerance or reliance. Randomization of patients between methadone administration and standard intra-operative narcotic administration allows for controlled and accurate investigation of subjects compared to the current standard of care.

• Clearly state target population and recruitment methods

We would screen the first 200 consecutive patients to determine whether inclusion criteria are met, with an end goal of 120 patients who will complete the study and 60 control subjects who receive the current standard of care in a 1:1 randomized fashion. Patient will be recruited in office at time of consent for surgery by the principal investigator.

• State inclusion/exclusion criteria clearly

Inclusion criteria:

Patients undergoing elective lumbar transforaminal interbody fusion or lumbar laminectomy and posterolateral fusion will be enrolled in the study and consented for intraoperative single-dose methadone administration or standard narcotic regimen administration in a 1:1 block randomization plan. Patient may undergo one or two spinal level fusions and in blocks of 5, will be assigned to intervention or control groups in a manner that will be blinded to both the clinical team and the patients.

o Exclusion criteria:

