• Describe predictors of interest along with potential confounders and effect modifiers Predictors of interest include drug abuse history and/or behavior, as well as anticipated benefit from history of medication usage in the literature. Potential confounders include previous narcotic use history, narcotic tolerance/dependence in patients not otherwise excluded during recruitment, variable pain thresholds and tolerance amongst different patients, duration and complexity of surgeries, as well as variable renal clearance. Many of these are also effect modifiers.

• Describe matching criteria, if applicable

Matching criteria will not be used at this study will be structured as a randomized control trial.

• Describe duration of follow-up, and timing of data collection

Post-operative imaging will be reviewed to determine successful decompression and instrumentation. Data collection will be done during patient's hospital stay. Patients will be asked about their post-operative pain at 4 hour intervals, and data regarding their overall narcotic usage and their time to ambulation will be recorded from the medical record. Follow-up will then consist of: 1 week for phone call by spine NP, 2 week evaluation as is standard for all post-operative patients.

• Describe the planned interventions and their timing.

A study participant will be randomized ahead of time to be administered methadone or the current standard of care in blocks of 5 blinded to clinical personnel. If the patient is assigned to the methadone group, the anesthesiology team will be given this information and the anesthesiologist assigned to the Revised 4/17/13, 6/23/15

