Two sample T-tests will be performed to evaluate continuous variables such a total morphine dose, pain level per VAS, time to first morphine dose, time to ambulation, and time to discharge. The assistance of a statistician, [name], from the Albert Einstein College of Medicine, Division of Biostatistics will be used for statistical analyses performed in this study. Wilcoxon Rank Sum Test will be used if outliers are noted in the study population, detected as more than 5 MAD from the median, and a concern presents that single patients may skew the data. Additionally, review of these patients who are outliers may also necessitate their exclusion from this work if they provide data that will significantly modify the mean of the remaining patients. This can be accounted for in the goal of 60 patients to be accrued in each arm of the study. A thorough explanation and review will performed on any such patients in any form of write up of this work.

At least one study hypothesis (or a statement that the study is hypothesis-generating or a feasibility study):

The use of single dose intraoperative methadone will decrease total narcotic usage, time to ambulation, mean pain rating at 24 and 48 hours and will decrease number of days of hospitalization compared to sufentanil (current standard of care) controls.

• A statement regarding specifically what data are to be used to test the hypothesis (or to generate the hypotheses)

We will obtain data of total narcotic usage, days until patients ambulate with physical therapy, pain ratings at 24 and 48 hours, and days to discharge, all obtained from the patient's medical record.

- o The statistical method(s) to be used to test the hypothesis with that data
 Two-sample T-test will be used with the assistance of an Albert Einstein statistician, [name], to analyze
 the above data and determine if there is statistical significance between the two groups, in addition to the
 stipulations outlined above to address outlier patients.
- A power analysis to determine the sample size (even for pilot studies)

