 We proposed to recruit 60 patients to undergo the new treatment and another 60 as controls. This gives us greater than 80% (95%) power to detect an improvement of 0.56 (0.74) within-group standard deviation at statistical significance level 0.05 as had been calculated to be 51 patients per group. Using 60 patients will ensure the usability of our data to detect differences of this effect sizes between groups. From our preliminary data, the standard deviation of time to discharge is 6.7 days, therefore, our sample size is able to detect an average reduction of 3.8 days (5.0 days) in time to discharge with 80% (95%) power.

Describe methods for interim analyses or early stopping, if applicable A data safety monitoring committee will be organized for the purposes of data evaluation in this study.

The members of the committee will include [name], neurosurgeon in the Department of Neurosurgery who performs spinal surgeries yet is not involved in the implementation of this project, and [name], statistician in the Department of Epidemiology and Population Health who is not involved in this protocol. After 20 patients complete the study (approximately 10 patients in each arm), interim analyses will be performed to compare pain ratings, narcotic usage, time to ambulation, and time to discharge to control patients, and the data safety monitoring committee will be asked to review all results and advise the study personnel as well as the IRB about study continuation. If there a significant increase in any of these measured values beyond a single standard deviation of the mean, the data safety monitoring committee and the IRB will come to a decision regarding continuation of the study. Assuming the outcome follows a normal distribution, with 10 patients in each arm, and under the null hypothesis that there is no difference between two groups, the chance of observing a difference greater than or equal to one standard deviation between two groups is about 1/100000. With four measures considered here, the overall Type I error will be no greater than 5/100000. Therefore, the loss of power from the

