interim analysis is negligible. If the methadone intervention contributes greater than normal adverse events (>2 patients) the study will be held from further recruitment. The study medication will not be administered further, no dosing changes will be made, and the IRB will be informed. A decision at this point will be reached regarding further accrual. If a patient should die prior to discharge, a thorough cause analysis will be implemented by the DSMB, the IRB, in addition to the analysis that will already be performed by the hospital. If it is due to the surgery outside of the trial mediation, the data for this patient will not be used and the information will be explicitly reported in any publication yet kept separated from the other patient's data, as it would not be feasible or make sense to include this patient in the analysis. If this adverse event is found to be caused by the methadone administration, the trial will be stopped. This is however an extremely unlikely scenario as methadone is used daily by millions of individuals, has already been approved by the FDA, and our study patients will undergo a rigorous screening, namely for QTc prolongation, to remove any potential risk of death as a result of methadone administration. The only wayy to address this possibility is to have a plan to remove this patient's data from the other patient's data, with a clear note made in the report.

Describe how possible confounding and/or effect modification will be addressed. The possible confounders have been addressed via the strict inclusion and exclusion criteria of the study. Other confounding variables including past narcotic usage, and a cutoff of <10mg equivalents of morphine will be considered when selecting patients for participation in this study. Such a low daily morphine dose is unlikely to significantly impact methadone effect or post-operative narcotic use in patients with this low level of narcotic usage compared to narcotic-naïve patients. Patient time to ambulation will be confounded by baseline neurological status and therefore we will randomly assigning patients to each arm of the study as described above. Confounding in regards to time of operative procedure and complexity of surgery will be controlled properly with appropriate randomization.

Describe how loss to follow up will be addressed

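### The continuous outcomes are compared without covariate adjustment although the plan itself names prognostic pre-operative factors; a prespecified adjusted model would gain precision at little cost

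*Combined protocol and SAP*

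**What the plan says.** Section 2, inclusion criteria: two operations are eligible (transforaminal interbody fusion, or laminectomy with posterolateral fusion), and "Patient may undergo one or two spinal level fusions". No stratification factor is named under randomisation.

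Section 2, predictors and confounders: the potential confounders include previous narcotic use and "duration and complexity of surgeries", and many of those listed are said to be effect modifiers too.

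Section 7, confounding: baseline neurological status is said to confound time to ambulation, and the answer given is random assignment. For complexity, "Confounding in regards to time of operative procedure and complexity of surgery will be controlled properly with appropriate randomization". Prior opioid use is handled by eligibility, and what remains below the limit is argued to matter little.

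Section 7a, method: "Two-sample T-test will be used" to "determine if there is statistical significance between the two groups". Section 3 plans the same test, and a rank-sum test replaces it if outliers appear. No regression, ANCOVA or other adjusted analysis appears anywhere.

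**The concern.** Randomisation balances prognostic factors on average, not in the one trial that is run. Number of levels, procedure type and neurological status are known before incision and may bear on opioid use, ambulation and stay. An unadjusted test leaves the variation they explain in the error term, while a model that contains them removes it and needs no more patients. Prespecification also matters. If the arms turn out visibly unequal in two-level cases, an adjustment chosen after the data are seen is open to challenge.

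For the questionnaires, section 2 speaks of improvement, which implies a change from baseline. A simple change score usually uses the baseline less efficiently than a model with the baseline as a covariate.

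**Working it through.** **1. The plan's own figure.** Section 7a claims "greater than 80% (95%) power to detect an improvement of 0.56 (0.74) within-group standard deviation"; its basis is 51 per group with alpha = 0.05. Sidedness is not stated. A two-sided t-test with d = 0.56, alpha = 0.05 and 80% power needs 51.03 per group, which matches 51; one-sided would need 40. In addition, "the standard deviation of time to discharge is 6.7 days", and 0.56 × 6.7 = 3.75 and 0.74 × 6.7 = 4.96, which match the stated 3.8 and 5.0 days. At the planned 60 per group, unadjusted power is 86.0% for 0.56 SD and 98.0% for 0.74 SD. The stated power is met without adjustment.

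**2. Effect of adjustment.** If the covariates explain a share R² of the outcome variance, the residual SD is multiplied by √(1 − R²). The standardised effect becomes 0.56/√(1 − R²), and 60 per arm is worth 60/(1 − R²). R² is not in the documents; the range is an assumption.

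| Assumed R² | 60 per arm is worth | Power at 0.56 SD | Discharge difference detectable with 80% power |
|---|---|---|---|
| 0 | 60.0 | 86.0% | 3.46 days |
| 0.02 | 61.2 | 86.7% | 3.42 days |
| 0.05 | 63.2 | 87.7% | 3.37 days |
| 0.10 | 66.7 | 89.4% | 3.28 days |
| 0.20 | 75.0 | 92.5% | 3.09 days |
| 0.30 | 85.7 | 95.3% | 2.89 days |

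**3. Cost of uninformative covariates.** The table does not charge for estimating the covariate effects. With N = 120 and p covariates, the variance is multiplied by about (N − 3)/(N − 3 − p). For p = 4 this is 117/113 = 1.035, an increase of about 3.5%. Break-even is R² = 4/117 = 0.034. For p = 2 (levels and procedure only) it is 2/117 = 0.017. At R² = 0.02 the gain is therefore nil or slightly negative; from about 0.05 upward it is positive.

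**4. Questionnaires.** With post-score variance 1 and baseline correlation r, the change score has variance 2(1 − r) and ANCOVA has 1 − r². At an assumed r of 0.5 these are 1.00 and 0.75; at 0.7 they are 0.60 and 0.51.

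**5. Chance imbalance.** With 60 per arm and an assumed 30-50% two-level cases, the arms differ by 10 percentage points or more in 27-32% of trials under individual randomisation.

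**The case against.** The strongest reply is that nothing is broken. Under individual randomisation the unadjusted t-test is unbiased, and its error rate already allows for chance imbalance. That stands. A reader might infer from the quoted sentence that the comparison is confounded or underpowered, but step 1 supports neither reading.

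The imbalance figure also sounds worse than it is. If two-level cases fared a full SD worse, a 10-point imbalance would move the contrast by 0.10 × 1 = 0.10 SD, against a standard error of √(2/60) = 0.18 SD.

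The gain may be small. For time to discharge, one evenly split factor explains R² only if its two groups differ by 2 × 6.7 × √R² days: 4.2 days for 10% and 7.3 days for 30%. Nothing in the documents shows differences of that size. This stands, and it is why the range starts at 2% and why the precision is not simply free.

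Two wider readings also fail. A reader might extend the point to every primary outcome. Disposition is categorical and has no stated test, and the questionnaires are not in section 7a's list of t-tested variables. Nor is prior opioid use wholly left to chance: patients at 10 mg morphine equivalent per day or more are excluded, and section 7 gives a reason for discounting the rest.

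What survives is that levels, procedure type and neurological status are not limited in that way, the protocol itself regards complexity and neurological status as confounders, and the possible loss from adjusting is small.

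**Conclusion.** The point holds as an efficiency recommendation for the continuous outcomes. Under the assumption that the covariates explain 2-30% of outcome variance, power at 0.56 SD with 60 per arm moves from 86% to about 87-95%, before the small cost of estimating the covariates. The worst case considered is about 3.5% more variance, if four covariates explain nothing.

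These figures treat patients as individually allocated. Section 2 instead sends each block of 5 to a single arm, which leaves 120/5 = 24 allocation units. A reader might infer that covariate adjustment would make good the reliance on randomisation. It would not. If outcomes correlate within blocks, an ordinary linear model does not correct the error term. At an assumed correlation of 0.05 the design effect is 1 + 4 × 0.05 = 1.2, and unadjusted power at 0.56 SD falls to about 79%. That is a separate problem and needs its own remedy.

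**What to change.** In section 7a:

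- Make the main analysis of each continuous outcome a prespecified linear model with arm, number of levels (one versus two) and procedure type.
- For time to ambulation, add baseline neurological status where it is recorded, and define the measure.
- For the questionnaires, use the baseline score as a covariate (ANCOVA). Do the same for pain where a baseline score is recorded.
- Treat prior opioid use (none versus any) as optional, since eligibility already limits it.
- Name the scale of each outcome in advance, and do not choose it after outliers have been seen.
- Keep the unadjusted t-test as a sensitivity analysis.

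Disposition needs its own stated method, outside this change.

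For levels and procedure type the cost is wording and a little analysis work; no patients are added and treatment does not change. The baseline scores may cost more. No pre-operative time point is stated for the questionnaires or for pain, so one would have to be specified and, if it is not already routine, collected.

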Appendix 1: Criteria for Exclusion of Minors from Research protocols

- 1. The research topic to be studied is irrelevant to children;
- 2. There are laws or regulations barring the inclusion of children in the research. For example, the regulations for protection of human subjects allow consenting adults to accept a higher level of risk than is permitted for children;
- 3. The knowledge being sought in the research is already available for children or will be obtained from another ongoing study, and an additional study will be redundant. NIH program staff can be contacted for guidance on this issue if the information is not readily available;
- 4. A separate, age-specific study in children is warranted and preferable (consult NIH Policy for specific example of such studies).
- 5. Insufficient data are available in adults to judge potential risk in children (in which case one of the research objectives could be to obtain sufficient adult data to make this judgment). While children usually should not be the initial group to be involved in research studies, in some instances, the nature and seriousness of the illness may warrant their participation earlier based on careful risk and benefit analysis.
- 6. Study designs aimed at collecting additional data on pre-enrolled adult study participants (e.g., longitudinal follow-up studies that did not include data on children).
- 7. Other special cases justified by the investigator and found acceptable to the review group and the Institute Director.
